6.4 EXCLUSION CRITERIA

The following items represent the exclusion criteria:

- 1. Any dermatological disorder, which in the investigator's opinion, may interfere with the accurate evaluation of the subject's skin characteristics, except for the study condition of acne.
- 2. Subjects who are not willing to use the assigned study device to their face as instructed.
- 3. Subjects who have used any topical prescription or OTC acne products for 2 weeks prior to study entry.
- 4. Subjects who have taken any oral prescription or OTC acne products for 4 weeks prior to study entry.
- 5. Subjects who have used a non-OTC cleanser without benzoyl peroxide, sulfur or salicylic acid for at least 2 weeks prior to study entry.
- 6. Subject who have not had any facial treatments in the past 6 months and are willing to withhold all facial treatments during the course of the study including facials, facial peels, photo facials, laser treatments, dermabrasion, botulinum toxin (Botox), injectable filler treatments, intense pulsed light (IPL), acid treatments, tightening treatments, and/or facial plastic surgery.
- 7. Subjects who are pregnant, breast feeding or planning a pregnancy.
- 8. Subjects with clinically significant and/or unstable medical disorders.
- 9. Subjects who are unwilling or unable to comply with the requirements of the protocol.
- 10. Subjects who have a history of a psychological illness or condition that would interfere with their ability to understand and follow the requirements of the study.
- 11. Subjects who have undergone recent facial surgery.
- 12. Subjects currently participating in any other clinical trial.
- 13. Subjects having started hormone replacement therapies (HRT) or hormones for birth control less than 3 months prior to the study entry; or who plan on starting, stopping or changing doses of HRT or hormones for birth control during the study.
- 14. Subjects who have a cardiac pacemaker, implanted defibrillator, or other implanted metallic or electronic device.
- 15. Subjects who are wearing EKG monitoring equipment.
- 16. Subjects with phlebitis, thrombophlebitis, broken capillaries, or varicose veins.
- 17. Subjects who have seizures, epilepsy, or cancer/tumors.
- 18. Subjects who have a history of hypertrophic scarring or keloid formation.

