5. STUDY DESIGN OVERVIEW

Male and female subjects will be enrolled in this single-site monadic study to evaluate the effect of a direct-current device on acne treatment. Subjects who sign the consent form and meet all inclusion criteria and none of the exclusion criteria will be enrolled at the baseline visit. Subjects will be asked to continue their self-selected moisturizer, non-medicated cleanser, and sunscreen they have used without difficulty for the prior 30 days and for the 12 week study. Subjects must also continue all facial products and cosmetics unchanged for the duration of the study. No other oral or topical acne products can be used. Subjects must be washed out of all topical acne products for at least 2 weeks and all oral acne products for at least 4 weeks. Subjects must possess mild to moderate acne with 5-30 inflammatory lesions and no nodules/cysts.

At baseline visit, subjects will receive the study acne device to be applied to the areas of the face afflicted by acne following cleansing, every other day. The dermatologist investigator will assess the face for the investigator global acne assessment (IGA) based on the following 5 point ordinal scale: 0=clear, 1=almost clear, 2=mild, 3=moderate, and 4=severe. In addition, the dermatologist investigator will perform an inflammatory and non-inflammatory lesion count. The dermatologist investigator will assess the tolerability of the device in terms of peeling, dryness, redness, and swelling on a 5-point ordinal scale (0=none, 1=minimal, 2=mild, 3=moderate, & 4=severe).

The subjects will assess device tolerability in terms of itching, burning, redness, and swelling. All assessments will be made on a 5-point ordinal scale (0=none, 1=minimal, 2=mild, 3=moderate, & 4=severe). Subjects will be given their diaries, study device, and electroconductive media and asked to return to the research center in 2 weeks. A reminder text will be sent to encourage compliance prior to the week 2 visit.

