6.3 INCLUSION CRITERIA

The following items represent the inclusion criteria:

- 1. Subjects with mild to moderate acne (5-30 inflammatory lesions and no nodules/cysts).
- 2. Male and female subjects age 18-50 years.
- 3. Subjects with all Fitzpatrick skin types.
- 4. Subjects of all complexion types (normal, oily, dry, combination).
- 5. Subjects who have used the same moisturizer without difficulty for 30 days and will continue using same moisturizer during the 12 week study.
- 6. Subjects agree not to introduce any new colored cosmetics (lipsticks, eye shadows, facial foundations, blush, & powder).
- 7. Subjects who are using no other acne products for the duration of the study.
- 8. No known medical conditions that, in the investigator's opinion, may interfere with study participation.
- 9. Women of childbearing potential must be willing to use a form of birth control during the study. For the purpose of this study, the following are considered acceptable methods of birth control: oral contraceptives, Norplant®, Depo-Provera®, double barrier methods (e.g., condom and spermicide) and abstinence.
- 10. Subjects have signed an Informed Consent Form in compliance with 21CFR, Part 50: "Protection of Human Subjects."
- 11. Subjects are dependable and able to follow directions and willing to comply with the schedule of visits.

12. Subjects in generally good physical and mental health.

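### Exclusion 5 is worded the wrong way round and its term non-OTC is ambiguous: it does not screen out cleansers with acne actives and may bar the subjects the design expects

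*Combined protocol and SAP*

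**What the plan says.** Section 6.4 opens with "The following items represent the exclusion criteria", and item 5 of that list reads "Subjects who have used a non-OTC cleanser without benzoyl peroxide, sulfur or salicylic acid for at least 2 weeks prior to study entry". The synopsis carries the same item in its own exclusion list. Section 5 gives the enrolment rule: "Subjects who sign the consent form and meet all inclusion criteria and none of the exclusion criteria will be enrolled at the baseline visit".

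The same section describes the cleanser history that the design expects. Subjects are asked to "continue their self-selected moisturizer, non-medicated cleanser, and sunscreen they have used without difficulty for the prior 30 days" and to keep using these products over the 12 weeks. The synopsis and section 7.2.1 say the same. Among the eligibility items, only inclusion 5 has a 30-day stability rule, and it covers one product: "Subjects who have used the same moisturizer without difficulty for 30 days and will continue using same moisturizer during the 12 week study".

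Other text deals with acne products in general:

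- Exclusion 3 bars "Subjects who have used any topical prescription or OTC acne products for 2 weeks prior to study entry".
- Inclusion 7 requires "Subjects who are using no other acne products for the duration of the study".
- The design text sets a topical washout of at least 2 weeks.
- Section 6.5 allows no acne product on study apart from the study products.

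None of these four mentions cleansers, and the protocol does not define what counts as an acne product.

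**The concern.** An exclusion criterion should name what disqualifies a subject. Item 5 names what ought to qualify one: at least 2 weeks on a cleanser free of the three actives. It is the only criterion that mentions cleansers or these actives, and it points the wrong way. Exclusion 6 has the same fault for facial treatments, which suggests that entry requirements were pasted into the exclusion list. Correcting item 6 would not correct item 5.

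Two things are at stake. The first is eligibility. Section 9.1 counts a subject as completed only if all entry criteria were satisfied, and section 14.5 rules out departures from the protocol short of a formal revision. Staff therefore cannot simply apply the presumed intent.

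The second is the efficacy comparison. The endpoint in section 12.5 is the change in IGA from baseline to week 12, and there is no concurrent arm. A change of cleanser around entry that affects acne cannot be told apart from a device effect.

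**Working it through.** This is mainly a check of wording. The plan gives no figure to reproduce here: section 12.1 says only that the sponsor chose 50 subjects.

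**Step 1: item 5 against the design text.** Non-medicated is taken to mean containing none of the three actives. The expected subject has 30 days on such a cleanser. Item 5 is triggered at 2 weeks, or 14 days, and 30 > 14, so the duration condition is always met. Whether the item applies then depends on non-OTC, which is not defined.

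| Cleanser history at entry | Item 5, if non-OTC = not an OTC drug product | Item 5, if non-OTC = prescription | Other criteria |
|---|---|---|---|
| Shop-bought plain cleanser, 30 days (what the design expects) | Barred | Not barred | No bar |
| Prescription cleanser without the actives, 30 days | Barred | Barred | Barred by exclusion 3 only if classed as an acne product |
| Wash with an active, classed as an acne product, used up to entry | Not barred | Not barred | Barred by exclusion 3 and the washout |
| Wash with an active, not classed as an acne product, used up to entry | Not barred | Not barred | Not clearly barred by any criterion; conflicts with the design text only |

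Under neither reading does item 5 act as the intended screen. The first row shows the contradiction with sections 5 and 7.2.1. The last row shows the gap that the other criteria leave.

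**Step 2: direction of any effect in the last row.** A long-used wash that does not change is already in the baseline value. One started shortly before entry could add improvement after baseline. One stopped at entry could let acne worsen and count against the device. The direction is not fixed.

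**Step 3: scale, under assumptions only.** Let f be the share of subjects whose wash changed around entry, and c the resulting improvement in standard deviations (SD) of the change score. Neither is in the documents. The mean change shifts by f × c. For a two-sided one-sample t test on change at 0.05 with n = 50, no device effect and an unchanged SD, the noncentrality is f × c × √50. With f = 10% (5 of 50) and c = 0.5, the shift is 0.10 × 0.5 = 0.05 SD and the noncentrality is 0.05 × 7.07 = 0.35. The chance of a significant result is then 0.064 instead of 0.050.

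| f | c = 0.25 | c = 0.5 | c = 1.0 |
|---|---|---|---|
| 5% | 0.051 | 0.053 | 0.064 |
| 10% | 0.053 | 0.064 | 0.107 |
| 20% | 0.064 | 0.107 | 0.284 |
| 50% | 0.139 | 0.410 | 0.934 |

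For comparison, n = 50 detects a mean change of 0.40 SD with 80% power and 0.47 SD with 90%. The t test is the type planned for lesion counts, taken here as paired. IGA is to be tested with the Wilcoxon signed rank test, so the table is only a rough guide for IGA. If washes were stopped, c would be negative and the shift would run against the device.

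**The case against.** The strongest reply is that this is a drafting slip with little room to do harm. Any cleanser that staff regard as an acne product is barred for 2 weeks before entry by exclusion 3 and the washout, and during the study by inclusion 7 and section 6.5. The study has one site, so uneven application between sites does not arise. No endpoint or test changes. All of this stands, and it limits the consequences. It does not make item 5 usable.

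A reader might go further than the text allows in four ways:

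- **Every intended subject is excluded.** This follows only if non-OTC means not an OTC drug product. If it means prescription, users of ordinary plain cleansers are not caught.
- **Without item 5 there is no look-back on cleansers at all.** Exclusion 3 and the washout still impose 2 weeks on those classed as acne products, and the design text still describes 30 days on a non-medicated cleanser.
- **Effects of medicated washes do carry into the 12-week change and flatter the device.** The documents do not show that such users would enter, or how many. The direction is open as well.
- **The rule on keeping facial products unchanged lets a subject stay on a medicated acne wash.** In context it does not. It follows the reference to a non-medicated cleanser and precedes the ban on other acne products.

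The point that inclusion 5 leaves out sunscreen is true but minor, since no bias from sunscreen follows from the documents.

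**Conclusion.** Exclusion 5 is reversed in both places where it appears, and non-OTC makes it ambiguous. That rests on the wording alone. It contradicts the 30-day non-medicated cleanser text in full under one reading of non-OTC. Under the other it bars fewer people but still fails to screen out the three actives. Since enrolment turns on these criteria, the item must be corrected.

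The effect on the efficacy result is a possible risk only. It is limited to washes that contain one of the actives, are not classed as acne products, and are started or stopped around entry. Each such subject is 1/50 = 2% of the sample. The number of them, and the size and sign of their effect, are not given. At the assumed shares of 5% to 20%, the false-positive rate in the illustration runs from 0.051 to 0.284, and the upper end needs 10 subjects each shifted by a full SD.

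**What to change.** Reword item 5 in the synopsis and in section 6.4 so that it excludes recent users of cleansers with the actives and keeps the protocol's own 2-week window. For example: *Use, within the 2 weeks before study entry, of any cleanser that contains salicylic acid, sulfur or benzoyl peroxide.* Naming the ingredients means that eligibility no longer depends on whether staff call the wash an acne product. Remove non-OTC, or define it.

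Then reconcile item 5 and inclusion 5 with the 30-day non-medicated cleanser text in the synopsis, section 5 and section 7.2.1. Either inclusion 5 should carry the cleanser requirement, or the design text should say that 30 days is an expectation and not an entry criterion. Adding sunscreen to inclusion 5 is optional. Exclusion 6 can be corrected in the same revision.

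The cost is a wording change in the criteria and the eligibility checklist, with the written sponsor and IRB approval that section 14.5 requires. A few subjects who recently switched cleanser may have to wait a short time before entry. No analysis changes.

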1. PROTOCOL SYNOPSIS

| Title of Study: | Evaluation of the Safety and Efficacy of an Acne Treatment Device |
|--|---|
| Study Period: | 12 weeks |
| Test Device and Application Instructions: | ZIIP Device (active) -400 microamps direct current, applied 3 days per week on non-consecutive days, on all areas afflicted by acne The following instructions will be provided: 1. Both silver probes must come in contact with skin throughout treatment. 2. Slowly make continuous circles with the top probe (the one farthest away from the charging port) over acne within each facial zone. **NOTE: Instructional video will be provided for participants to follow** 3. Treat each facial zone for 1 minute. Your device will beep and vibrate at the one minute mark to indicate that treatment of that zone is complete. Only treat the acne zone(s) identified for treatment. 4. After treatment, wipe your device clean with a tissue, being careful to avoid the charging port. Spray the device and a second tissue lightly with rubbing alcohol and wipe again, remaining careful to avoid the charging port. 5. Store safely away from water, moisture or debris. |
| Ancillary Product and Application Instructions: Objective: | Electroconductive Media Apply as a thin layer to all facial areas afflicted with acne The objective of this study is to demonstrate the safety and efficacy of a novel direct |
| Objective. | current device employed in the treatment of mild to moderate inflammatory acne after 12 weeks of every other day use. |
| Design: | Male and female subjects will be enrolled in this single-site monadic study to evaluate the effect of a device on acne treatment. Subjects who sign the consent form and meet all inclusion criteria and none of the exclusion criteria will be enrolled at the baseline visit. Subjects will be asked to continue use of their self-selected moisturizer, non-medicated cleanser, and sunscreen they have used without difficulty for the prior 30 days and for the 12-week study. Subjects must also continue all facial products and cosmetics unchanged for the duration of the study. No other oral or topical acne products can be used. Subjects must be washed out of all topical acne products for at least 2 weeks and all oral acne products for at least 4 weeks prior to study participation. Subjects must possess mild to moderate acne with 5-30 inflammatory lesions and no nodules/cysts. |

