6.5 CONCOMITANT MEDICATIONS

All oral and topical prescription medications should remain unchanged during the study. No oral or topical over the counter or prescription acne medications are allowed. No other acne products other than the study products are allowed during the study.

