7.1.2 MEDICAL HISTORY

An abbreviated medical history including current medications shall be recorded.

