7.1.3 DERMATOLOGICAL EXAMINATION

A dermatological examination shall be performed to insure subjects possess acne and meet all inclusion criteria and none of the exclusion criteria.

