7.2 STUDY CONDUCT PROCEDURES

7.2.1 BASELINE

Male and female subjects will be enrolled in this single-site monadic study to evaluate the effect of a direct current device on acne treatment. Subjects who sign the informed consent form and meet all inclusion criteria and none of the exclusion criteria will be enrolled at the baseline visit. Subjects will be asked to continue their self-selected moisturizer, nonmedicated cleanser, and sunscreen they have used without difficulty for the prior 30 days and for the 12 week study. Subjects must also continue all facial products and cosmetics unchanged for the duration of the study. No other oral or topical acne products can be used. Subjects must be washed out of all topical acne products for at least 2 weeks and all oral acne products for at least 4 weeks. Subjects must possess mild to moderate acne with 5-30 inflammatory lesions and no nodules/cysts.

At baseline visit, the dermatologist investigator will assess the face for the investigator global acne assessment (IGA) based on the following 5 point ordinal scale: 0=clear, 1=almost clear, 2=mild, 3=moderate, and 4=severe. In addition, the dermatologist investigator will perform an inflammatory and noninflammatory lesion count within each facial quadrant (zone). The subjects will then be provided the study device and electroconductive media for every other day use after cleansing to the acne afflicted facial zones. The first use of the device will occur at the research center to ensure all subjects are using the device properly.

The dermatologist investigator will assess the tolerability of the device in terms of peeling, dryness, redness, and swelling on a 5-point ordinal scale (0=none, 1=minimal, 2=mild, 3=moderate, and 4=severe). The subjects will then assess device tolerability in terms of itching, burning, redness, and swelling. All assessments will be made on a 5-point ordinal scale (0=none, 1=minimal, 2=mild, 3=moderate, and 4=severe). Subjects will be given their diaries and asked to return to the research center in 2 weeks. A reminder text will be sent to encourage compliance prior to the week 2 visit.

All investigator selected subjects will be photographed with the Canfield VISIA CR using Standard 1 lighting at baseline, week 2, week 4, and week 8, and week 12.

7.2.2 WEEK 2

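### Exclusion item 6 is worded as an entry requirement, so as written it bars the subjects it evidently means to admit and does not exclude recently treated or unwilling ones

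*Combined protocol and SAP*

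**What the plan says.** Item 6 stands in the exclusion list of the synopsis and again in Section 6.4, with the same wording: "Subject who have not had any facial treatments in the past 6 months and are willing to withhold all facial treatments". It goes on to say that the withholding applies throughout the study, and gives an illustrative list that runs from facials and peels through laser, intense pulsed light, dermabrasion, botulinum toxin and fillers to facial plastic surgery.

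The exclusion list is operative. The synopsis (Design), Section 5 and Section 7.2.1 state that subjects who sign consent and "meet all inclusion criteria and none of the exclusion criteria will be enrolled at the baseline visit". Section 7.1.3 has the dermatological examination confirm that subjects "possess acne and meet all inclusion criteria and none of the exclusion criteria".

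The inclusion lists (synopsis and Section 6.3) contain no criterion on facial treatments.

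**The concern.** An exclusion criterion should describe the person to be kept out. Item 2 of the same list does so by naming subjects who will not use the device as instructed. Item 6 describes the person to be let in. Its form, a past condition joined to a future undertaking, is that of inclusion item 5: "Subjects who have used the same moisturizer without difficulty for 30 days and will continue using same moisturizer during the 12 week study". The likeliest explanation is that an inclusion criterion was placed under the wrong heading.

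The slip matters because of the design. All subjects use the active device, and Section 12.5 defines efficacy as improvement in IGA at week 12 compared with baseline. With no concurrent control arm, a cosmetic or dermatological procedure shortly before baseline or during the 12 weeks could change IGA or lesion counts, and the change would be read as a device effect or would mask one. Item 6 is evidently meant to prevent this.

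**Working it through.** The plan gives no figure on this point, so the check is logical: what item 6 does as written, and whether any other text does its job.

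**1. Item 6 as written and as evidently meant.** Let U = no facial treatment in the past 6 months, and W = willing to withhold facial treatments during the study. Item 6 describes U and W together. As an exclusion it removes subjects with (U and W). As an entry requirement it would remove subjects with not (U and W), which is (not U) or (not W).

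| Subject | Item 6 as written (exclusion) | Same sentence as an entry requirement |
|---|---|---|
| Untreated, willing | Excluded | Eligible |
| Untreated, unwilling | Not excluded by item 6 | Ineligible |
| Treated, willing | Not excluded by item 6 | Ineligible |
| Treated, unwilling | Not excluded by item 6 | Ineligible |

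The two columns are opposite in all four rows.

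**2. Whether other text restores the restriction.**

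- Exclusion 11, "Subjects who have undergone recent facial surgery", covers surgery only, and does not say how recent.
- Exclusion 9 removes those who will not comply with the protocol's requirements. The only text about withholding facial treatments is item 6 itself, so exclusion 9 has nothing else to enforce here.
- Section 6.5 keeps oral and topical prescription medication constant and adds: "No other acne products other than the study products are allowed during the study". Section 7.2.1 says: "Subjects must also continue all facial products and cosmetics unchanged for the duration of the study". These are rules about products. How far they reach into facials, peels or acid treatments is arguable. They do not reach laser, intense pulsed light, dermabrasion, botulinum toxin or fillers.

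So for those procedures the only pre-study window and the only on-study restriction lie in item 6.

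**3. Whether such procedures would be recorded.** Section 7.1.2 says: "An abbreviated medical history including current medications shall be recorded". The visit schedule in Section 2 has a brief history and medication review at all five visits. The diary in Section 8.1 covers device and conductive-media use plus comments. A procedure might come to light through any of these, but none asks for it.

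**4. Logical bounds, with 50 subjects planned.**

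- Text followed literally: every untreated and willing volunteer is turned away, so all 50 would be recently treated, unwilling to withhold, or both.
- Screening by evident intent: 0 of 50 would be recently treated or unwilling, but all 50 would meet exclusion 6 as printed.

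These bounds follow from the wording alone. They do not predict what the site will do and they are not an effect size.

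**The case against.** The strongest answer is that nobody would apply item 6 literally. This is a single-site study, the protocol is the site's own document, and the same organisation supplies all study documents (Section 14.2) and performs the analysis (Section 12). No second site has to interpret the text, and the intended meaning is plain. Section 7.1.6 speaks loosely of the ability to meet the inclusion and exclusion criteria together, which fits treating item 6 as a condition to be met. This stands as far as it goes: screening by intent is likely, and the bias is then avoided. It does not override the enrolment rule stated in four places. Section 14.5 allows no deviation without a revision approved in writing by the sponsor and the IRB.

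Three stronger readings are tempting, and the documents do not support them.

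- A reader might infer that the trial will enrol the wrong population. That requires the site to reject every untreated, willing volunteer, which is a logical extreme.
- A reader might infer that the efficacy result is biased. The documents give no frequency, direction or size for the effect of such procedures on IGA or lesion counts. Exclusion 11 and the product rules also cover part of the list.
- A reader might infer damage to the analysis because Section 9.1 defines a completed subject as one who satisfied all entry criteria. Section 12 defines no completer or per-protocol population, so no planned analysis depends on that status.

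**Conclusion.** Item 6 is wrong as written. It is an internal inconsistency in an operative eligibility rule, of moderate severity. Taken with the enrolment rule, it bars untreated, willing subjects and does not exclude recently treated or unwilling ones, and no other text restricts the device-based and injected procedures it lists.

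The consequence depends on how the site screens. If the text is followed literally, the uncontrolled week-12 comparison with baseline is open to confounding of unknown size and direction. If the site screens by intent, which is the likelier case, the efficacy comparison is protected. What remains is formal but real: enrolled subjects meet a listed exclusion, contrary to Section 14.5.

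This rests on two assumptions: that item 6 was meant as an entry requirement, which its wording strongly suggests, and that the screening form, which is not in the documents, does not already correct it.

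**What to change.** Correct item 6 in both the synopsis and Section 6.4, in one of two ways.

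- Move it unchanged to the inclusion lists (synopsis and Section 6.3).
- Leave it among the exclusions and reverse it: exclude subjects who have had any facial treatments in the past 6 months, or who are unwilling to withhold all facial treatments during the study, including those now listed.

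By step 1 of the check, the two are logically equivalent provided that the reversed wording keeps the sponsor's own 6-month window and open-ended list. A version limited to the named treatments would narrow the criterion.

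Obtain the written sponsor and IRB approval that Section 14.5 requires before implementation, and check that the screening form matches the corrected text. The cost is a wording change in two places plus that approval and check. Visits, sample size and analysis are unaffected.
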